12.4 Return Product Analysis

Sponsor representatives and their contact information are provided in the Manual of Procedures that accompanies this protocol.

Document: TDOC-0053541 **Version:** 3.0; Most-Recent; Effective; CURRENT

Status: Effective Page 56 of 59

Alcon study products associated with Device Deficiencies and/or product-related AEs should be returned and must include the Complaint # which will be provided by the Sponsor after the case is entered in the Sponsor's Global Product Complaint Management System.

12.5 Unmasking of the Study Treatment

Masked information on the identity of the assigned medical device should not be disclosed during the study (see Section 9.4 for details on the masking procedure). If the treatment code needs to be broken in the interest of subject safety, the Investigator is encouraged to contact an appropriate Sponsor representative prior to unmasking the information if there is sufficient time. Dependent upon the individual circumstances (ie, medical emergency), the code may be broken prior to contact with the Sponsor. The Sponsor must be informed of all cases in which the code was broken and of the circumstances involved. Additionally, the Sponsor may be required to unmask the information in order to fulfill expedited regulatory reporting requirements.

12.6 Follow-Up of Subjects with Adverse Events

The Investigator is responsible for adequate and safe medical care of subjects during the study and for ensuring that appropriate medical care and relevant follow-up procedures are maintained after the study.

The Investigator should provide the Sponsor with any new safety information (which includes new AEs and changes to previously reported AEs) that may affect the safety evaluation of the device. For AEs that are unresolved/ongoing at the time of subject's exit from the study, any additional information received at follow up should be documented in the eCRFs up to study completion (ie, database lock).

All complaints received after this time period will be considered and processed as spontaneous (following the post-market vigilance procedures) and should be communicated to the medical device's manufacturer as per local requirements.

The Investigator should also report complaints on non-Alcon products directly to the manufacturer as per the manufacturer's instructions or local regulatory requirements.

12.7 Pregnancy in the Clinical Study

Pregnancy is not reportable as an AE; however, complications may be reportable and will be decided on a case—by-case basis.

Document: TDOC-0053541 **Version:** 3.0; Most-Recent; Effective; CURRENT

Status: Effective Page 57 of 59

13 DATA HANDLING AND ADMINISTRATIVE REQUIREMENTS

13.1 Completion of Source Documents and Case Report Forms

The nature and location of all source documents will be identified to ensure that original data required to complete the eCRFs exist and are accessible for verification by the investigational site monitor. If electronic records are maintained, the method of verification must be determined in advance of starting the study. At a minimum, source documents should include the following information for each subject:

Subject identification (name, sex, race/ethnicity)

Documentation of subject eligibility

Date of Informed Consent

Dates of visits

Documentation that protocol specific procedures were performed

Results of study parameters, as required by the protocol

Study product accountability records

Documentation of AEs and other safety parameters (if applicable)

Records regarding medical histories and the use of concomitant therapies prior to and during the study

Date of study completion and reason for early discontinuation, if applicable

It is required that the author of an entry in the source documents be identifiable. Direct access to source documentation (medical records) must be allowed for the purpose of verifying that the data recorded on the eCRF are consistent with the original source data.

The eCRFs will be provided to the investigational sites; only designated individuals may complete the eCRFs. The eCRFs will be submitted at regular intervals based upon the clinical study visit schedule. It is expected that all data reported will have corresponding entries in the source documents and that the Principal Investigator will review the reported data and certify that the eCRFs are accurate and complete. No subject identifiers should be recorded on the eCRFs beyond subject number, and demographic information.

13.2 Data Review and Clarifications

The eCRF data will be reviewed against the subject's source data by the study monitors to ensure completeness and accuracy. After monitoring has occurred at the investigational sites

Print Date:

Document: TDOC-0053541 **Version:** 3.0; Most-Recent; Effective; CURRENT

Status: Effective Page 58 of 59

and the eCRFs have been submitted, additional data clarifications and/or additions may be needed. Data clarifications and/or additions are documented and are part of each subject's eCRFs.

13.3 Regulatory Documentation and Records Retention

The Investigator is required to maintain up-to-date, complete regulatory documentation as indicated by the Sponsor and the Investigator's files will be reviewed as part of the ongoing study monitoring. Financial information is not subject to regulatory inspection and should be kept separately.

Additionally, the Investigator must keep study records and source documents until the Sponsor provides written approval for their destruction. If the Investigator retires, relocates, or for any other reason withdraws from responsibility of keeping the study records, the Sponsor must be notified and suitable arrangements made for retention of study records and source documents needed to comply with national and international regulations (generally 2 years after discontinuing clinical development or after the **latest** marketing approval).

The results of the study are intended for publication to support future product information.

13.4 Quality Assurance and Quality Control

The Sponsor will be responsible for implementing and maintaining quality assurance and quality control systems to ensure the study is conducted and data are generated, documented and reported in compliance with the protocol, GCP and applicable regulatory requirements. The Sponsor will secure agreement from all involved parties to ensure direct access to the study-related investigational site, source data and documents, and reports for the purpose of monitoring and auditing by the Sponsor, and inspection by domestic and foreign regulatory authorities. Quality control will be applied to each stage of data handling to ensure that all data are reliable and have been processed correctly. Agreements made by the Sponsor with the Investigator/Institution and any other parties involved in the clinical study will be provided in writing as part of the protocol or as a separate agreement.

Document: TDOC-0053541 **Version:** 3.0; Most-Recent; Effective; CURRENT

Status: Effective Page 59 of 59

Document: TDOC-0054746 **Version:** 2.0; Effective; CURRENT

Status: Effective

Short Title:

Effective Date: 03-Jul-2018

Statistical Analysis Plan CLL541-P001

Full Title:

Statistical Analysis Plan CLL541-P001 / NCT03169153

Protocol Title: One-month clinical comparison of silicone hydrogel monthly

lenses in high lipid depositors

Project Number: CLL541-P001/ NCT03169153

Reference Number:

Protocol TDOC Number: TDOC-0053541

Author:

Template Version: Version 4.0, approved 16MAR2015

Approvals: See last page for electronic approvals.

Job Notes:

This is the second revision (Version 3.0) of the Statistical Analysis Plan for this study. This version of the Statistical Analysis Plan is based on Version 2.0 and Version 3.0 of the study protocol.

Document: TDOC-0054746 **Version:** 2.0; Effective; CURRENT

Status: Effective

Executive Summary:

Key Objective:

To demonstrate superiority of AIR OPTIX® plus HydraGlyde (AOHG) compared with ACUVUE® VITA® (VITA) in total lipid uptake (total of surface and bulk uptake) after 30 days of wear by high lipid depositors.

Effective Date: 03-Jul-2018

Decision Criteria for Study Success:

Success of this study will be based on demonstration of superiority of AOHG compared with VITA in total lipid uptake (total of surface and bulk uptake) after 30 days of wear by high lipid depositors.

Document: TDOC-0054746 **Version:** 2.0; Effective; CURRENT

Status: Effective

Table of Contents

Statistic	cal Analysis Plan CLL541-P001	1
Table o	f Contents	3
List of	Γables	4
List of 1	Figures	4
1	Study Objectives and Design	5
1.1	Study Objectives	
1.2	Study Description	
1.3	Randomization	7
1.4	Masking	7
1.5	Interim Analysis	7
2	Analysis Sets	7
2.1	Safety Analysis Set	7
2.2	Full Analysis Set (FAS)	7
2.3	Per Protocol (PP) Analysis Set	7
3	Subject Characteristics and Study Conduct Summaries	7
4	Effectiveness Analysis Strategy	8
4.1	Efficacy Endpoints	8
4.2	Effectiveness Hypotheses	10
4.3	Statistical Methods for Effectiveness Analyses	11
4.3.1	Primary Effectiveness Analyses	
		11 12
		13
4.6	Interim Analysis for Efficacy	
5	Safety Analysis Strategy	
5.1	Safety Endpoints	
5.2	Safety Hypotheses	
5.3	Statistical Methods for Safety Analyses	
5.3.1	Adverse Events	
5.3.2	Biomicroscopy Findings/Slit Lamp Examination	

Alcon - Bus Document: TD Status: Effective		Effective Date: 03-Jul-2018
5.3.3	Device Deficiencies	15
6 A	Analysis Strategy for Other Endpoints	15
7 S	Sample Size and Power Calculations	15
8 I	References	16

1.1 Study Objectives

PRIMARY OBJECTIVE

The primary aim of the study is to confirm that a silicone hydrogel contact lens that attracts lower levels of total lipids *in vitro* (AOHG) also attracts lower levels of total lipids *in vivo* compared with a silicone hydrogel contact lens with high *in vitro* lipid attraction (VITA) in habitual high lipid depositor lens wearers. Therefore, the primary objective is to demonstrate superiority of AOHG compared with VITA in total lipid uptake (total of surface and bulk uptake) after 30 days of wear by high lipid depositors.

Effective Date: 03-Jul-2018

Document: TDOC-0054746 **Version:** 2.0; Effective; CURRENT

Status: Effective

1.2 Study Description

Key components of the study are summarized in Table 1-1.

[figure not shown]
Table 1-1 Study Description Summary

Study Design	Single-site, prospective, randomized, double-masked, crossover study
Study Population	Volunteer subjects at least 18 years of age who wear monthly replacement silicone hydrogel lens and are classified as high lipid depositors. Required: 70 completed (35/sequence) Planned: Approximately 78 randomized and approximately 140 screened/enrolled
Number of Sites	1 (United Kingdom)
Test Product AIR OPTIX® plus HydraGlyde (AOHG)	
Control Product	ACUVUE® VITA® (VITA)
Duration of Treatment	Test Product:30 (+3) days per period; Control Product: 30 (+3) days per period
Visits	Visit 1 (Screening 1/Baseline) Visit 2 (Screening 2) Visit 3 (Day 1 - Insertion Period 1)* Visit 4 (Day 30 + 3 Period 1) Visit 5 (Day 1 - Insertion Period 2) Visit 6 (Day 30 + 3 Period 2/Study Exit) *Randomization will occur at Visit 3 (Day 1)

Effective Date: 03-Jul-2018

A study design schematic is depicted in Error! Reference source not found.

Figure .1–1 Study Design

Document: TDOC-0054746 **Version:** 2.0; Effective; CURRENT

Status: Effective

1.3 Randomization

A member of the Randomization Programming group at Alcon who is not part of the study team will generate the randomized allocation schedule(s) for study lens sequence assignment. Randomization will be implemented in iMedidata Balance.

Effective Date: 03-Jul-2018

1.4 Masking

This study is double-masked.

1.5 Interim Analysis

No interim analyses are planned for this study.

2 Analysis Sets

2.1 Safety Analysis Set

Safety analyses will be conducted using the Safety Analysis Set on a treatment-emergent basis. The Safety Analysis Set will include all subjects/eyes exposed to any study lenses (AOHG or VITA) evaluated in this study. Subjects who are lost to follow-up and their exposure to dispensed study lenses is unknown will be included in the safety data set. For treatment-emergent safety analyses, subjects/eyes will be categorized under the actual lens exposed in the corresponding lens sequence.

Adverse events occurring from the time of informed consent but prior to first exposure to study lenses (AOHG or VITA) will be summarized in subject listings.

2.2 Full Analysis Set (FAS)

The FAS is the set of all randomized subjects who are exposed to any study lenses (AOHG or VITA) evaluated in this study.

2.3 Per Protocol (PP) Analysis Set

The PP Analysis Set is a subset of all randomized subjects and excludes all data/subjects that meet any of the critical deviation or non-evaluable criteria identified in the Deviations and Evaluability Plan.

3 Subject Characteristics and Study Conduct Summaries

The following tables will be presented:

- Subject Disposition by Lens Sequence
- Analysis Sets by Lens
- Analysis Sets by Lens Sequence

Document: TDOC-0054746 **Version:** 2.0; Effective; CURRENT

Status: Effective

Subject Accounting by Lens Sequence

- Demographics Characteristics by Lens Sequence
- Baseline Characteristics by Lens Sequence [habitual lens VA, habitual lens care solution]

Effective Date: 03-Jul-2018

In addition, the following subject listings will be provided:

- Listing of Subjects Excluded from Protocol Defined Analysis Sets
- Listing of Lens Sequence Assignment
- Listing of Subjects Discontinued from Study

4 Effectiveness Analysis Strategy

This study defines 1 primary, endpoints. All effectiveness evaluations will use the FAS as the primary analysis set.

Supportive analyses of the primary effectiveness endpoints will be conducted using the PP Analysis Set only if the number of subjects excluded from the PP Analysis Set exceeds 5% of the FAS.

For all planned inferential analyses, alternative models/methods may be considered if convergence cannot be achieved. Furthermore, if significant carryover effects are noted (confounded with sequence effect), results will be examined by period to ensure the overall conclusion is valid.

All data obtained in evaluable subjects/eyes will be included in the analysis. No imputation for missing values will be carried out for the effectiveness analysis.

4.1 Efficacy Endpoints

[figure not shown]
Primary Endpoint

The primary endpoint is the total amount of lipids (µg) absorbed/adsorbed and extracted (total of surface and bulk uptake) from worn test and control lenses at Day 30. Only OD lenses will be used for the *ex vivo* analysis.

Document: TDOC-0054746 **Version:** 2.0; Effective; CURRENT

Status: Effective

Document: TDOC-0054746 **Version:** 2.0; Effective; CURRENT

Status: Effective

4.2 Effectiveness Hypotheses

Primary Effectiveness

[figure not shown]
The null and alternative hypotheses are formulated as follows:

Ho:
$$\mu_T - \mu_C \ge 0$$

Ha: $\mu_T - \mu_C \le 0$

where μ_T and μ_C represent the mean total lipid uptake (total of surface and bulk uptake) measured from the test and control lenses, respectively.

Effective Date: 03-Jul-2018

Document: TDOC-0054746 **Version:** 2.0; Effective; CURRENT

Status: Effective

Effective Date: 03-Jul-2018

4.3 Statistical Methods for Effectiveness Analyses

4.3.1 Primary Effectiveness Analyses

A mixed effect repeated measures model will be fit to test these hypotheses.	

Document: TDOC-0054746 **Version:** 2.0; Effective; CURRENT

Status: Effective

Effective Date: 03-Jul-2018

4.6 Interim Analysis for Efficacy

There are no plans to conduct an interim analysis and no criteria by which the study would be terminated early based upon statistical determination.

5 Safety Analysis Strategy

5.1 Safety Endpoints

The safety endpoints are

- Adverse events
- Biomicroscopy Findings/Slit Lamp Examination
 - o Limbal hyperemia
 - o Bulbar hyperemia
 - Conjunctival compression/indentation
 - o Chemosis
 - Corneal vascularization
 - Palpebral conjunctival observations
 - o Corneal infiltrates
 - o Anterior Segment Inflammation
 - Other findings
 - Bulbar Conjunctival staining
 - Corneal staining
- Device deficiencies

5.2 Safety Hypotheses

There are no formal safety hypotheses in this study. The focus of the safety analysis will be a comprehensive descriptive assessment of safety endpoints listed in Section 5.1.

5.3 Statistical Methods for Safety Analyses

The analysis set for all safety analyses is the safety analysis set as defined in Section 2.1. Safety variables will be summarized descriptively. Baseline will be defined as the last

Document: TDOC-0054746 **Version:** 2.0; Effective; CURRENT

Status: Effective

measurement prior to exposure to study lens. For biomicroscopy data, baseline will be defined as Visit 3 for Period 1 and Visit 5 for Period 2.

Effective Date: 03-Jul-2018

5.3.1 Adverse Events

The applicable definition of an Adverse Event (AE) is in the study protocol. All AEs occurring from when a subject signs informed consent to when a subject exits the study will be accounted for in the reporting.

Analysis and presentation of pre-treatment and between-treatment AEs will be separated from treatment-emergent AEs occurring during the study periods. A pre-treatment AE is an event that occurs after signing informed consent but prior to exposure to study lenses (AOHG or VITA). A between-treatment AE is an event that occurs after last exposure to Period 1 lenses but prior to exposure to Period 2 lenses. The period for treatment-emergent AE analysis starts from exposure to the study lenses for Period 1 or Period 2 until the subject completes or is discontinued from the study.

The following tables and supportive listings will be provided:

- Incidence of All Ocular Treatment-Emergent Adverse Events
- Incidence of All Nonocular Treatment-Emergent Adverse Events
- Incidence of Serious Ocular Treatment-Emergent Adverse Events
- Incidence of Serious Nonocular Treatmen-Emergent Adverse Events
- Listing of All Ocular Treatment-Emergent Adverse Events
- Listing of All Nonocular Treatment-Emergent Adverse Events
- Listing of All Ocular Pre-Treatment Adverse Events
- Listing of All Nonocular Pre-Treatment Adverse Events
- Listing of All Ocular Between-Treatment Adverse Events
- Listing of All Nonocular Between-Treatment Adverse Events

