Each safety variable will be summarized descriptively. AEs will be classified as pre-treatment, treatment-emergent, or between-period. Counts and percentages will be provided by relationship to lens, and separate tables will be generated for ocular and nonocular AEs. Counts and percentages in each grade category will be presented for each Biomicroscopy parameter. Device Deficiencies will also be tabulated. Supporting subject listings describing details of each safety variable will be provided. No inferential testing will be performed for the safety analysis.

Sample Size Calculation

Sample size calculation for the primary effectiveness endpoint (1-sided, α =0.05) is summarized below:

Primary Endpoint	Assumptions	Power	N/sequence group
Total lipid uptake (total of surface and bulk uptake)	SD paired differences = 13.88 Detectable difference = 10	80%	7

Document: TDOC-0053541 **Version:** 3.0; Most-Recent; Effective; CURRENT

Status: Effective Page 11 of 59

Effective Date: 07-Dec-2017

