11.7. Safety Analysis

The safety endpoints for this study are Biomicroscopy Findings, AEs, and Device Deficiencies.

Descriptive summaries (counts and percentages) for ocular and nonocular AEs will be presented by Medical Dictionary for Regulatory Activities (MedDRA) Preferred Terms. In addition to an overall presentation of AEs, relationship to lens will be identified. Serious Adverse Events will also be tabulated separately. Individual subject listings will be provided, as necessary.

Additionally, individual subject listings will be provided for AEs that:

Occur after signing the Informed Consent Form, but prior to exposure to test or control lenses (pre-treatment)

Occur after last exposure to Period 1 lenses, but prior to exposure to Period 2 lenses (between-period)

Each Biomicroscopy parameter will be tabulated by its grade. Counts and percentages of eyes that experience an increase of ≥ 2 grades from Visit 3/Visit 5 to any subsequent visit within each period will be presented. A supportive listing will be generated which will include all Biomicroscopy data from the visits within each affected period for those eyes experiencing the increase of ≥ 2 grades, with the following variables: lens, Investigator, subject, age, sex, visit, eye, parameter, baseline value, and value at the visit.

Frequency counts will be tabulated for each Device Deficiency category. Additionally, 2 listings will be provided: prior to exposure to study lens and treatment-emergent.

No inferential testing will be done for the safety analysis.

Document: TDOC-0053541 **Version:** 3.0; Most-Recent; Effective; CURRENT

Status: Effective Page 50 of 59

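### Does SAP 5.3.1 miscount adverse events by lens because its treatment-emergent window has no Period 1 end and gap events go only to listings?

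*SAP*

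**What the plan says.** SAP 5.3.1 sorts AEs into three groups: pre-treatment, between-treatment and treatment-emergent.

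- It first states the separation: "Analysis and presentation of pre-treatment and between-treatment AEs will be separated from treatment-emergent AEs occurring during the study periods".
- It then defines the gap group: "A between-treatment AE is an event that occurs after last exposure to Period 1 lenses but prior to exposure to Period 2 lenses".
- The next sentence says the treatment-emergent period "starts from exposure to the study lenses for Period 1 or Period 2 until the subject completes or is discontinued from the study".
- It also promises that "All AEs occurring from when a subject signs informed consent to when a subject exits the study will be accounted for in the reporting".

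The incidence tables named there are all treatment-emergent, for example "Incidence of Serious Ocular Treatment-Emergent Adverse Events". Gap events get listings, for example "Listing of All Ocular Between-Treatment Adverse Events".

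The protocol uses the same gap category. Section 11.7 assigns those events to individual subject listings, and it adds that "Serious Adverse Events will also be tabulated separately". The synopsis says "Counts and percentages will be provided by relationship to lens". Protocol 11.2.1 and SAP 2.1 both put safety analyses on a treatment-emergent footing and place the data under the lens the subject actually wore.

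**The concern.** The window sentence names two possible starts and only one kind of end, which is leaving the study. Taken by itself, it lets the Period 1 window run through the gap and all of Period 2. A Period 2 event would then count for both lenses, and a gap event would be treatment-emergent and between-treatment at once.

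The other rule has a cost of its own. If gap events go to listings only, an ocular event that starts the day after Period 1 lenses come off enters no incidence table, even if it is serious and judged related. The protocol's sentence on serious events does not itself carry a treatment-emergent limit, and no output title in the SAP mentions relationship to lens.

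There is no safety hypothesis test, so the descriptive tables are the whole safety result. If events were assigned to the wrong lens, nothing later in the analysis would correct it.

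**Working it through.** The documents give no AE rate, so there is no AE figure to reproduce. The check uses the visit schedule, an illustration with assumed rates, and the text.

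**Inputs**
- Each period lasts 30 (+3) days (Protocol 10.1). Protocol 9.2 prints ±3 instead; the conclusion does not depend on which applies.
- The gap from Visit 4 to Visit 5 is 1 to 14 days (Protocol 10.2.4).
- Allocation to sequences is 1:1 (Protocol 9).
- In the gap, subjects wear glasses or their usual lenses (Protocol 9.2). Exclusion criterion 2 rules out anyone whose usual lens is AOHG or VITA.
- Assumed, not from the documents: AE rates of 5% and 10% per period for the two lenses.

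**Step 1: the window sentence read alone**
- Shortest Period 1 window: 30 + 1 + 30 = 61 days.
- Longest: 33 + 14 + 33 = 80 days.
- Ratio to days of wear: 61/30 = 2.03; 80/33 = 2.42; with a 30-day period and a 14-day gap, 74/30 = 2.47.

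**Step 2: what that reading would do to the rates**

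Each lens is the Period 1 lens in half the subjects. There it would collect its own events plus the other lens's Period 2 events:
- lower-rate lens: 0.5 × (5% + 10%) + 0.5 × 5% = 10%;
- higher-rate lens: 0.5 × (10% + 5%) + 0.5 × 10% = 12.5%;
- ratio: 12.5/10 = 1.25, against a true 2.0.

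Counting gap events as well, at the average rate of 7.5% per 30 days, adds 0.5 × 7.5% × g/30 to each lens for a gap of g days. With g = 1 the rates are 10.1% and 12.6%. With g = 14 they are 11.75% and 14.25%, a ratio of 1.21. The distortion would be real if anyone analysed the data this way.

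**Step 3: the same paragraph read whole**

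| Onset | Rule that applies | Where it counts |
|---|---|---|
| During Period 1 wear | Window opens at Period 1 exposure; lens-worn rule | Period 1 lens |
| In the gap | Between-treatment definition and the separation sentence | Listing |
| During Period 2 wear | Window opens at Period 2 exposure; lens-worn rule | Period 2 lens |

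The separation sentence ties treatment-emergent events to the study periods, so the gap is out. The lens-worn rule then settles Period 2. The lens rates become 0.5 × 5% + 0.5 × 5% = 5% and 0.5 × 10% + 0.5 × 10% = 10%, so the true ratio of 2.0 is recovered.

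**Step 4: what listing the gap events costs**

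As a share of the time from Period 1 insertion to Period 2 insertion, the gap is between 1/(33 + 1) = 2.9% and 14/(30 + 14) = 31.8%. As a share of the time from first insertion to exit, it is between 1/67 = 1.5% and 14/74 = 18.9%.

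Suppose a fraction f of each lens's events appears only after removal. The loss applies only where that lens came first, so each rate is multiplied by 1 − f/2. With the same f for both lenses, both rates fall and their ratio is unchanged.

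**Step 5: serious events and relationship**

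Protocol 11.2.1 sets the treatment-emergent basis for safety analyses as a whole, so the protocol's serious-event table can be read within it, and the SAP does so. The SAP gives output titles, not table layouts. A title that omits relationship does not show that the breakdown is missing from the table, and the protocol's commitment to it stands.

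**The case for a change.** The strongest case is that the per-period reading has to be inferred. The SAP spells out a period-specific baseline for biomicroscopy and does not do the same for AEs. The lens-worn rule speaks of subjects and eyes rather than events by onset, and in a crossover every completer wears both lenses.

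There is also a wrinkle at the visit itself. At Visits 4 and 6 the lenses come off before the slit-lamp examination. Taken strictly, a finding first seen at that examination could be called between-treatment at Visit 4 and treatment-emergent at Visit 6.

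It stands that the sentence lacks a Period 1 end, and that a serious gap event would be seen only in a listing. The rest carries little weight:

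- The alternative reading would require an analyst to ignore the separation and the gap definition stated immediately before the window sentence.
- Grade increases of 2 or more at the Visit 4 examination are counted for Period 1 whatever their AE label, because that table runs from Visit 3 or Visit 5 to any later visit within the period (Protocol 11.7, SAP 5.3.2). A finding seen straight after about ten hours of wear would ordinarily be dated to the wear.
- Counting Period 2 events to exit gives that period almost no extra time, since lens removal and exit both occur at Visit 6.
- Extending the Period 1 window over the gap would make the two windows unequal, up to 33 + 14 = 47 days against 33. It would also bring in events that arose on usual lenses. A main window that stops at last exposure would leave gap events out just as the present rule does.

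**Conclusion.** No change to the plan follows. The double counting, the 61- to 80-day window and the fall from a 2-fold to about a 1.25-fold difference appear only when one sentence is detached from its paragraph. With the gap rule and the lens-worn rule applied, each event belongs to one lens or to the listings, and the on-lens rates are right.

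Listing gap events is a fair trade-off that the protocol makes openly. It keeps time off the study lenses out of the lens rates, and every event is still reported with its causality assessment. The cost is bounded by a gap of 1 to 14 days and falls about equally on the two lenses.

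This rests on three assumptions: analysts take the paragraph as a whole, late-appearing events form a similar share for both lenses, and the sequences stay roughly balanced. If the late share differed between lenses, the gap listings would show it. The stated safety aim is to collect and describe, there is no safety inference, and the lipid endpoint is untouched, so no study conclusion depends on this wording.
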